## 2 HYPOTHESIS

We hypothesize that MK2 pathway blockade during active COVID-19 infection in hospitalized patients will result in improvement in respiratory-failure free survival.

### 3 OBJECTIVES AND ENDPOINTS

#### 3.1 OBJECTIVES

##### 3.1.1 Primary Objectives

To assess the efficacy of ATI-450 on hypoxic respiratory failure-free survival in patients with moderate-severe COVID-19

##### 3.1.2 Secondary Objectives

To assess the clinical efficacy of ATI-450 on respiratory function and survival in patients with moderate-severe COVID-19

To assess the safety of ATI-450 in patients with moderate-severe COVID-19.

To assess the anti-inflammatory and immune effect of ATI-450

#### 3.2 ENDPOINTS

To assess the pharmacodynamics of ATI-450 in patients with moderate-severe COVID-19 (based on changes in cytokine and biomarkers)

##### 3.2.1 PRIMARY ENDPOINT

What is being measured	Measurement time frame	Measurement Tool
Proportion of responders on Day 14 defined as all subjects who are alive, free of respiratory failure (do not require supplemental oxygen) and do not experience negative intercurrent events by Day 14 of the trial will be considered responders. 	Study Day 14	Noted in patient medical record or Day 14 Follow-up call

 Patients with pre-existing oxygen requirements who return to at least their baseline pre-COVID-19 infection oxygenation level will be considered to have successfully achieved the respiratory-free failure survival endpoint.

##### 3.2.2 Secondary Endpoints

What is being measured	Measurement time frame	Measurement Tool
Change in 7 point-ordinal scale	Baseline, Day 3, Day 7, Day 14, Day 28 and follow-up.	Using WHO COVID-19 Ordinal scale measuring: Proportion and time to patients with greater than 2 point improvement on the 7 point categorical scale

Change in oxygen saturation-normalization	Baseline and continuous throughout hospitalization	Peripheral capillary pulse oximeter to measure: SpO 2 /FiO 2 ratio over time, sustainment of normalization in 24 hours, and relative shifts in SpO 2 /FiO 2 categories (<235, between 235 and 315, greater than 315) over time
Need for advanced respiratory care	Baseline and continuous throughout hospitalization	Derived from medical record: time of intubation in the ICU, duration of ICU care in days, duration of overall hospitalization in days
All-cause mortality	Baseline and through d60	Noted in patient medical record
Number and percent of adverse events (AEs) and serious adverse events (SAEs); mean change from baseline lab values, vital signs, and ECG	Baseline through day 14 or at discharge <d14, at d28 ±3, d45 ±3 and d60 ±3 (lab values will be examined up to d45) 	CTCAE v5.0; changes in CBC, CMP, Mg, PT/INR, PTT, GGT, hsCRP, D-dimer, LDH, ferritin, creatine kinase, troponin-i, procalcitonin; standard vital signs measurement with pulse ox; ECG
Proportion of participants with normalization of fever for 24h	Baseline through day 14 or at discharge <d14	Standard daily vital measurement and obtained from patient medical record
Development of new bacterial or fungal infection (AE of Special Interest)	Continuous throughout hospitalization	Noted in patient medical record
Incidence of ARDS  through day 14 or at discharge <d14	From day 1 though day 14 or at discharge <d14	Noted in patient medical record
Change in plasma cytokines IL-1β, IL-6, IL-8 and TNF-α	Baseline, day 3, day 7 (or discharge <d7), day 14 (or discharge >d7 and <d14)	Plasma collected from blood and assayed on Luminex panel performed by KUMC BBV Core

 For clarification, lab values will be collected at baseline, day 3, day 7 (or discharge <d7), day 14 (or discharge >d7 and <d14), at day 28 ±3, day 45 ±3. Vital signs, pulse ox will be collected baseline through day 14 or at discharge <d14, at d28 ±3, d45 ±3 and d60 ±3 (lab values will be examined up to d45)

 ARDS Criteria:

- PaO2/FiO2 ≤ 300 (adjusted for barometric pressure).
- Bilateral infiltrates consistent with pulmonary edema on frontal chest radiograph.
- Requirement for positive pressure ventilation via endotracheal tube.
- No clinical evidence of left atrial hypertension. If measured, pulmonary arterial wedge pressure ≤ 18 mmHg.

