## PROTOCOL SUMMARY

Title	A double-blind, randomized controlled trial of ATI-450 in patients with moderate-severe COVID-19
Protocol Number	IIT-2020-ATI-450-COVID-19
Phase	2a
Design	Phase 2a, randomized, double-blind, placebo controlled, parallel group study in patients with moderate to severe COVID-19
Study Duration	9 months
Study Center(s)	The University of Kansas Medical Center
Objectives	
Primary Objective To assess the efficacy of ATI-450 on hypoxic respiratory failure-free survival in patients with moderate-severe COVID-19
 
Secondary Objectives To assess the clinical efficacy of ATI-450 on respiratory function and survival in patients with moderate-severe COVID-19
 
To assess the anti-inflammatory and immune effect of ATI-450
 
To assess the safety of ATI-450 in patients with moderate-severe COVID-19
 
Exploratory Objective To assess the pharmacodynamics of ATI-450 in patients with moderate-severe COVID-19

Number of Participants	20
Diagnosis and Main Inclusion Criteria	
Has laboratory-confirmed COVID-19 coronavirus infection as determined by polymerase chain reaction (PCR), or other commercial or public health assay in nasopharyngeal testing within 14 days of enrollment AND,
 
Hospitalized as a result of symptoms and signs related to COVID-19 infection, and ≤14 days since positive test AND:
 
Evidence of hypoxic respiratory failure: SpO2 ≤93% on room air or supplemental oxygen, or SpO2 ≥93% requiring ≥ 2L O2, or PaO2/FiO2 ratio <300mmHg, or tachypnea (respiratory rate ≥ 30 breaths/min) and
 
Evidence of pulmonary involvement by chest imaging or pulmonary exam

Study Product(s), Dose, Route, Regimen	
Dose of ATI-450
 
50 mg (as determined from Phase I study) per dose. (100 mg per day).
 
or
 
Placebo

	
Route Oral tablet
 
Schedule Pill will be taken twice daily preferably spaced 12 ±1 hours apart.

Duration of Administration	Up to a maximum of 14 days while inpatient. Patients discharged home or new requirement for mechanical ventilation will be discontinued off drug permanently.
Interim Monitoring	The study will be monitored at appropriate intervals, no less than those assigned per risk level designation, to assure compliance to GCP and to assess the data quality and study integrity.

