## 9 TREATMENT PLAN

The study drug / placebo will be administered within a 14-day cycle. Treatment will be administered to patients while they are hospitalized and will continue their 14-day course of medication as an inpatient. If the patient is discharged alive before treatment is completed, the patient will discontinue drug / placebo but remain on study.

Reported adverse events and potential risks are described in Adverse Events section.

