### 9.1 Treatment Regimen

#### 9.1.1 Treatment Plan

##### Drug Treatment Schedule

Pre-medications	None
Dose of ATI-450 or Placebo	1 tablet – placebo or 50 mg (as determined from Phase I study) (100 mg total per day).
Route	Oral tablet
Duration of Administration	Up to 14 days while inpatient or if appropriate for discharge home then drug or placebo will be discontinued on last day of being in the hospital
Schedule	Pill will be taken twice daily preferably spaced $12 \pm 1$ hours apart

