### 12.1 Adverse Event Monitoring

Medical history adverse events are recorded and graded using Common Terminology Criteria for Adverse Events (CTCAE) version 5.0. Serious adverse event and adverse event monitoring begins after initiation of study treatment and continues until the Day 60 safety follow-up. This Day 60 follow-up check and will be done by phone.

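### The infection and ARDS endpoints stop counting at discharge, so time at risk depends on recovery; both need a fixed window

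*Protocol*

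**What the plan says.** Section 3.2.2 of the protocol gives each secondary endpoint a time frame. New bacterial or fungal infection is counted "continuous throughout hospitalization", with no day limit and no period after discharge. Incidence of ARDS is counted "From day 1 though day 14 or at discharge <d14". The footnoted ARDS criteria include "Requirement for positive pressure ventilation via endotracheal tube", so a case after discharge implies readmission. In the same table, all-cause mortality runs to Day 60, and the general adverse event row has time points at Days 28, 45 and 60.

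For a patient sent home early, the Drug Treatment Schedule in Section 9.1.1 says that "drug or placebo will be discontinued on last day of being in the hospital", and Section 9 says that "the patient will discontinue drug / placebo but remain on study". Section 10.2.1 requires a phone call to patients discharged before Day 14, covering vital status, oxygen need and new adverse events. Section 12.1 says that adverse event monitoring "continues until the Day 60 safety follow-up"; Section 12.2 and Appendix A agree. Section 16.2.1 instead ends collection 30 days after the last dose. It also makes every new bacterial or fungal infection reportable as an AESI whatever its severity.

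The SAP lists neither infection nor ARDS among its outcome measures. Its safety assessment is adverse events, tabulated in a format set by the DSMB.

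**The concern.** Discharge is not a neutral cut-off here. Protocol 15.5 treats early discharge due to recovery as a positive intercurrent event, the SAP makes time to discharge a secondary efficacy measure, and Section 1.2 names reduced hospital occupancy as an aim. The plan thus allows that treatment may shorten the stay, and then uses the stay as the observation window for two other endpoints. A drug that only sent patients home sooner would lower both counts without changing the risk of either event.

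Take a patient discharged on Day 5 and readmitted on Day 10 with bacterial pneumonia. On a plain reading this patient is event-free for the infection endpoint. The infection row may have been meant to cover readmissions, but it does not say so. Section 15.5 also carries the primary endpoint's missing-data rule over to categorical secondary endpoints, and under that rule a value missing after a recovery discharge counts in the patient's favour. If applied to these two endpoints, it would record early leavers as event-free.

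Infection matters most. It is the only AESI, Section 1.3.1 lists it as a possible risk, and the Protocol Summary names drug-related infection under its stopping rules. An unequal window could make a real excess look smaller.

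**Working it through.** The documents give no rate, precision or sample size for either endpoint, so there is no stated figure to reproduce. The check compares the windows and then illustrates the mechanism.

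**Windows side by side**

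| Item | Starts | Ends |
|---|---|---|
| Infection endpoint (3.2.2) | not stated | discharge |
| ARDS endpoint (3.2.2) | Day 1 | Day 14, or discharge if earlier |
| Primary endpoint (3.2.1) | – | Day 14, by call if discharged |
| Mortality (3.2.2) | baseline | Day 60 |
| Adverse events (12.1, 12.2, Appendix A) | start of treatment | Day 60 |
| Adverse events (16.2.1) | start of treatment | 30 days after last dose |
| Treatment-emergent events (15.3) | first dose | 30 days after last dose |

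Only the first two rows depend on the discharge date itself. The two windows based on last dose still run well past discharge for an early leaver.

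**Illustration for infection.** All inputs are assumed. The one anchor is the protocol's 50% placebo response at Day 14 (15.1), used as a stand-in for the share of placebo patients discharged early.

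- Share discharged early, *q*: 50% placebo; 60%, 70% or 75% active.
- Early leavers go home on Day 5, 7 or 10; the others on Day 14, 20 or 28.
- 60-day infection risk *R*: 10% or 20%, the same in both arms, with a constant hazard that discharge does not change.

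Daily hazard: λ = −ln(1 − *R*)/60.
Proportion counted: *q*(1 − e^(−λ·d_early)) + (1 − *q*)(1 − e^(−λ·d_late)).

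One case, with *R* = 20%, Day 7 or Day 20, and 50% versus 70% discharged early:

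- λ = −ln(0.80)/60 = 0.003719 per day.
- Counted among early leavers: 1 − e^(−0.003719 × 7) = 2.57%.
- Counted among the others: 1 − e^(−0.003719 × 20) = 7.17%.
- Placebo: 0.5 × 2.57% + 0.5 × 7.17% = 4.87%.
- Active: 0.7 × 2.57% + 0.3 × 7.17% = 3.95%.
- Apparent risk ratio: 3.95/4.87 = 0.81, although the true hazard ratio is 1.
- With a true hazard ratio of 1.5, the apparent ratio is about 1.20.

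Over all combinations:

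- The lowest ratio is 0.65 (*R* = 10%, Day 5 or 28, 75% early on active: 2.84% versus 1.86%).
- The highest is 0.97 (*R* = 20%, Day 10 or 14, 60% early: 4.36% versus 4.22%).
- The hospital window counts about 17% to 34% of the placebo arm's 60-day events.

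**Fixed window.** Through Day 28 with *R* = 20%, both arms give 1 − e^(−0.003719 × 28) = 9.89%, ratio 1.00.

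**ARDS.** The Day 14 cap shrinks the effect. With the same hazard, early leavers on Day 7, everyone else followed to Day 14, and 50% versus 70% early, the result is 3.82% versus 3.32%, ratio 0.87.

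**Size in this trial.** At 10 per arm the worked case differs by 10 × (0.0487 − 0.0395) = 0.09 events. The largest gap on the grid (*R* = 20%, Day 5 or 28, 75% early) is 10 × (0.0587 − 0.0385) = 0.20 events.

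**Does Day 28 fit the adverse event windows?** The earliest possible last dose is Day 1, and 1 + 30 = Day 31. Day 28 therefore lies inside both stated windows; Day 60 lies inside only the Section 12.1 window for a patient whose last dose is before Day 30, which under the 14-day treatment limit is everyone.

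**The case against.** The strongest reply is that nothing is lost. Section 16.2.1 makes a post-discharge infection a reportable AESI with no restriction to hospital, Section 15.3 tabulates it as treatment-emergent up to 30 days after the last dose, and Section 10.2.1 provides a call that asks about it. A readmission with intubation by Day 14 is a negative intercurrent event under Section 15.5, so it already counts against its arm in the primary analysis. The SAP analyses neither endpoint separately, its sample size section disclaims between-group estimation, and the expected distortion is a fraction of one event. An in-hospital window based on chart-verified events is also an understandable choice for a pilot.

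Most of this stands. A reader might infer from the two rows that post-discharge events go unrecorded; the documents do not support that. A reader might also infer that both windows close at the moment drug stops. That is true only for patients discharged by Day 14 while still on drug. Treatment is otherwise given "Up to a maximum of 14 days while inpatient", and Section 11.4 withdraws it for intubation or serious infection. The infection window can then run on after treatment, so patients with long stays add off-drug time at risk.

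What does not stand is the defence of the window as a matter of preference. A count whose observation time is set by another outcome is a flawed measure, whatever the sample size. The same table and the primary endpoint show that fixed horizons were feasible.

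**Conclusion.** The point holds as a defect in how two secondary endpoints are defined. Their windows end at discharge, time at risk depends on recovery, and the endpoint counts leave out events after early discharge that the trial collects elsewhere. The direction follows from the definition: with equal hazards, the arm discharged earlier shows the lower rate.

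The size, an apparent risk ratio of 0.65 to 0.97, rests on assumed stays, an assumed infection risk, a hazard that discharge does not change, and no allowance for death. If infection is in truth more frequent in hospital, a shorter stay would prevent some infections. A fixed window would show that as a real difference, while the hospital window cannot separate it from shorter observation.

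A reader might infer that this trial's safety comparison will be biased. The documents do not support that: at about 10 per arm the gap is at most 0.2 of an event, and the SAP text plans no comparison of these endpoints. The SAP's attached table shells are not among the documents, so whether infection has its own row there is unknown. The practical effect falls on any report that follows the protocol's endpoint table. The change is worth making because it is cheap and concerns the only AESI.

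**What to change.** In Protocol 3.2.2, replace both time frames with a fixed window for every dosed patient, whatever the discharge date:

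- **Infection:** first dose through Day 28, from the AESI and adverse event records. The Day 28 visit has a 3-day margin and may fall on Day 25, so ask about the remaining days at the Day 45 contact.
- **ARDS:** first dose through Day 14, including readmissions, from the readmitting hospital's records. A phone call cannot supply the blood gas and radiograph that the criteria need; the call only identifies the readmission.

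For each, show events before and after discharge separately, and give the number of deaths within the window, since death also ends time at risk. Add a line to the SAP safety summary naming both endpoints, their windows and the FAS. This adds two outcomes that the SAP does not now list.

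Reconcile the adverse event collection windows (Day 60 in Sections 12.1, 12.2 and Appendix A; 30 days after last dose in 16.2.1). List infections to Day 60 only once that is settled; the Day 28 count need not wait for it.

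The cost is two table rows and a SAP line, with no new visit. The small downside is that post-discharge infections will rest partly on patient report and outside records, which the split by discharge makes visible.

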## 1.2 Rationale

ATI-450 is an oral small molecule MK2 inhibitor that potently inhibits multiple inflammatory cytokines (TNF $\alpha$ , IL1 $\beta$ , IL6 and IL8). It has been established to be well tolerated, with a good PK/PD profile, in Phase 1. ATI-450 is Phase 2 ready.

COVID-19 morbidity and mortality has been associated with Cytokine Release Syndrome (CRS) and Acute Respiratory Distress Syndrome (ARDS). Therapies such as anti-IL6 monoclonal antibodies appear to be effective CRS treatments in the critical care environment, based on their potent inhibition of a single cytokine target. By potently inhibiting multiple cytokines involved in CRS, ATI-450 may offer a viable and effective approach to managing this condition. There is clearly a need to develop additional therapeutic options to reduce morbidity/mortality and meet healthcare resource needs.

We propose that ATI-450 is developed initially as a potential treatment for patients hospitalized with COVID-19 related CRS. We aim to explore if ATI-450 can improve clinical symptoms and signs in such patients, with an

additional aim of reducing healthcare utilization by preventing progression to mechanical ventilation and/or reducing hospital occupancy.

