##### **Secondary Efficacy Analyses**

Supportive analyses will be conducted on the secondary efficacy endpoints described in Section 3.5. Categorical variables will be analyzed using a logistic regression like that described for the primary endpoint. In addition to the point estimate and confidence interval for the difference in proportions for categorical endpoints, odds ratios, corresponding confidence intervals and p-values will be provided. For categorical measures that are recorded over time, separate logistic regression analyses will be conducted at each timepoint.

Continuous secondary efficacy endpoints will be analyzed using a mixed model repeated measures MMRM analysis. The MMRM will include factors for treatment, baseline age group, gender, and scheduled timepoint as well as a random effect for patient. Model based means for each treatment group, model based differences between treatment groups will be provided over time as well as their corresponding confidence intervals and relevant p-values.

For time-to-event data, a two-sided stratified log-rank test will be applied. The stratification factor will be baseline age group (<60 versus  $\geq 60$ ). Estimates of the 25th, 75th percentile and the median (50th percentile) will be provided for each treatment group. Kaplan-Meier Curves and corresponding 95% confidence intervals will be provided as well as p-values based on the stratified log-rank test.

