#### 15.5 Intercurrent Events and Missing Data

An intercurrent event is one that occurs after the first dose of study medication and either precludes the observation of the variable or affects its interpretation. The following is a list of negative intercurrent events related to the primary endpoint:

- Death
- Withdrawal from study
- Intubation and ventilation
- Rescue with a non-protocol specified treatment for cytokine release syndrome

The following is a list of positive intercurrent events related to the primary endpoint:

- Early discharge due to recovery

The patient will be considered a responder if the primary endpoint is missing following a positive intercurrent event. Patients will be considered a non-responder for all observations (missing or not missing) following a negative intercurrent event.

Missing data and intercurrent event imputation will be treated in a similar manner as the primary endpoint for secondary endpoints of a categorical nature. For secondary endpoints of a continuous nature, the last observation prior to the intercurrent event will be carried forward (LOCF) for all positive intercurrent events and the worst observation prior to the intercurrent event will be carried forward (WOCF) for all negative intercurrent events.

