The primary objective is to assess the efficacy of ATI-450 on hypoxic respiratory failure-free survival in patients with moderate-severe COVID-19 pneumonia at day 14.

Secondary Objectives:

- To assess the clinical efficacy of ATI-450 on respiratory function and survival in patients with moderate-severe COVID-19 pneumonia.
- To assess the safety of ATI-450 in patients with moderate-severe COVID-19 pneumonia.

Exploratory Objectives:

- To Assess the pharmacodynamics of ATI-450 in patients with moderate-severe COVID-19 pneumonia.

Outcome Measures

Primary Efficacy Measure

- Primary treatment responder: defined as any patient who is alive, free of respiratory failure (does not require supplemental oxygen (greater than pre-existing use)) and does not experience a negative intercurrent event on Day 14 of the trial.

An intercurrent event is one that occurs after the first dose of study medication and either precludes the observation of the primary variable/endpoint or affects its interpretation. The following is a list of negative intercurrent events that could occur during this study:

- Death
- Withdrawal from study
- Intubation and ventilation
- Rescue with a non-protocol specified treatment for cytokine release syndrome

The following is a list of positive intercurrent events that could occur during this study:

- Early hospital discharge due to recovery

A patient will be considered a treatment responder if the primary endpoint is missing following a positive intercurrent event. A patient will be considered a treatment non-responder for all observations (missing or not missing) following a negative intercurrent event.

Secondary Efficacy Measures

- Change from baseline in the WHO COVID-19 7-point ordinal scale over time (**BASELINE, DAY 7, DAY 14, DAY 28**).
- All-cause mortality through Day 60 (**DAY 7, DAY 14, DAY 28 AND FOLLOW-UP**.).
- Responder based on 7-point ordinal scale: Greater than 2-point improvement from baseline on the 7-point ordinal scale. (**BASELINE, DAY 7, DAY 14, DAY 28 AND FOLLOW-UP**.).
- Time to discharge from the hospital.

Safety assessments include:

- Adverse events

Exploratory measures include:

- Change in serum cytokine Interleukin (IL)-6 over time (baseline, d7, EOT, d28).
- Change in serum cytokine IL-8 over time (baseline, d7, EOT, d28).
- Change in serum cytokines IL-1 β over time (baseline, d7, EOT, d28).
- Change in serum cytokine Tumor Necrosis Factor (TNF- α) over time.

*EOT: end of treatment

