Descriptive statistics (number of observations, mean (standard deviation) or median (minimum, maximum)) will be provided for continuous variables, and counts and percentages will be presented for categorical variables for each group.

Primary Efficacy Analysis

The study is hypothesis generating. The primary assessment of efficacy for this study will be the point estimate and corresponding exact 90% confidence interval for the proportions of responders for the ATI-450 and Placebo groups. All subjects who are alive, free of respiratory failure (do not require supplemental oxygen) by Day 14 of the trial will be considered responders. The point estimate and corresponding 90% confidence interval will be derived based on sample proportions and the Copper-Pearson CIs for proportions for the two groups (categorical data analysis by Alan Agresti, 3rd edition).

Secondary Efficacy Analyses

Binary variables will be analyzed using the method like that described for the primary endpoint. In addition to the point estimate and confidence interval for the difference in proportions for binary endpoints, odds ratios, corresponding confidence intervals will be provided. For binary measures that are recorded over time, separate analyses will be conducted at each timepoint.

Continuous secondary efficacy endpoints will be analyzed by estimating group means and mean difference and 95% CIs at each time point. Missing data will be imputed with the single imputation methods described above (LOCF or WOCF).

For time to discharge from hospital, estimates of the median (50th percentile) will be provided for each treatment group and Kaplan-Meier Curves will be provided. A two-sided stratified log-rank test will be applied. The stratification factor will be baseline age group (<60 versus ≥ 60).

Exploratory Outcomes Analyses

For all the Cytokines, changes over time (baseline, d7, EOT, d28) will be summarized by descriptive statistics and trajectory plots. Any time point after the end of treatment (EOT) will not be measured.

Safety Summaries

AEs will be summarized using table format based on DSMB requirements (attached).

Missing Data Imputation

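### The protocol's ICU and hospital durations have no rule for a stay that ends in death, and worst-observation-carried-forward does not supply one

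*Protocol*

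**What the plan says.** Protocol 3.2.2, in the row on need for advanced respiratory care, takes from the medical record "duration of ICU care in days, duration of overall hospitalization in days". It does not say what value a patient who dies receives. Section 1.2 makes the favourable direction clear, since one aim is "preventing progression to mechanical ventilation and/or reducing hospital occupancy".

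Protocol 15.5 introduces its event list with the words "The following is a list of negative intercurrent events related to the primary endpoint". The list is death, withdrawal, intubation and ventilation, and rescue treatment for cytokine release syndrome. For continuous secondary endpoints the section then says that "the worst observation prior to the intercurrent event will be carried forward (WOCF) for all negative intercurrent events".

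Protocol 15.3 offers two methods that could apply. One is "Continuous secondary efficacy endpoints will be analyzed using a mixed model repeated measures MMRM analysis". The other is "For time-to-event data, a two-sided stratified log-rank test will be applied". It does not say which of them covers the two durations.

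The SAP, dated 3/27/23, lists neither duration. Its only measure of stay is "Time to discharge from the hospital", and its method section says "For time to discharge from hospital, estimates of the median (50th percentile) will be provided for each treatment group", with Kaplan-Meier curves and an age-stratified log-rank test. It does not say how a death enters that analysis. For continuous secondary endpoints it replaces the repeated-measures model with group means and mean differences at each time point, and keeps the carried-forward rules.

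**The concern.** A day count rewards leaving hospital for any reason, including death. Suppose patient A dies in ICU on Day 4, scoring 4 ICU days and 4 hospital days. Patient B spends 6 days in ICU and goes home on Day 12, scoring 6 and 12. Patient A looks better on both measures.

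An arm with more early deaths can therefore appear to use less ICU and hospital care, and the protocol names reduced healthcare utilization as a long-range benefit (1.3.2). The protocol does have a rule for values affected by death. A reader may assume that it penalises death here, and it does not.

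**Working it through.** The documents give no power, precision or effect size for these durations, so there is no stated figure to reproduce. The check has four steps. The 10 patients per arm come from the SAP. All mortality rates and lengths of stay are assumptions.

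**1. Direction and size of the bias.** Let d of 10 patients die on day t and let survivors stay L days. Mean days used = [d × t + (10 − d) × L] / 10. The difference from an arm with no deaths and the same survivor stay is d × (t − L) / 10.

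- L = 14, t = 3, d = 3: (9 + 98) / 10 = 10.7 against 14.0, which is 3.3 days shorter.
- L = 10, t = 7, d = 1: (7 + 90) / 10 = 9.7 against 10.0, which is 0.3 days shorter.

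Over L of 10 or 14, t of 3, 5 or 7 and d of 1 to 3 (18 combinations), the arm with deaths always looks better, by 0.3 to 3.3 days.

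**2. The worst-observation rule.** For a running count where more days is worse, the worst value before death on day t is t. The means are the same in all 18 combinations. Intubation is also a listed negative event. Read literally, a patient intubated on day 3 who survives and stays 30 days would be scored about 3 days. The rule leaves deaths uncorrected and can shorten the stay of a very sick survivor.

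**3. Effect of chance with 10 per arm.** Expected difference in mean days used = (difference in mortality) × (mean stay of patients who die − mean stay of survivors). The simulation used gamma stays (shape 4), a survivor mean of 12 days and truncation at 28 days. Figures are for the higher-mortality arm.

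| Mortality | Mean stay, deaths | Difference in mean days | Looks better in |
|---|---|---|---|
| 30% v 10% | 6 days | 0.2 × (6 − 12) = −1.2 | 68% of trials |
| 40% v 10% | 6 days | 0.3 × (6 − 12) = −1.8 | 76% |
| 30% v 10% | 9 days | 0.2 × (9 − 12) = −0.6 | 59% |
| 40% v 10% | 9 days | 0.3 × (9 − 12) = −0.9 | 64% |

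If patients who die also stay 12 days on average, the difference is 0.2 × (12 − 12) = 0. If they stay 15 days, it is 0.2 × (15 − 12) = +0.6, and the bias reverses.

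With hospital-free days through Day 28 and death scored 0, a survivor averages 28 − 12 = 16. The higher-mortality arm is then 0.2 × 16 = 3.2 or 0.3 × 16 = 4.8 days worse on the mean, and looks better in only 19% or 10% of trials. The Hodges-Lehmann difference behaves alike: about 3.0 and 4.8 days worse, with the same 19% and 10%.

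**4. The SAP endpoint.** Take 3 deaths on day 5 and single discharges on days 8 to 14.

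- Deaths censored at death: 7 remain at risk and the curve falls from 4/7 to 3/7 on day 11, so the median is 11 days.
- Deaths kept as never discharged to day 60: the curve reaches 5/10 on day 12, so the median is 12 days, with 70% ever discharged.
- Death counted as the end of stay: the curve reaches 5/10 on day 9, so the median is 9 days.

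Only the third choice gives deaths the shortest values. The SAP does not say which applies.

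**The case against.** The strongest reply is that the protocol defers analysis details to the SAP, and the SAP contains neither duration. A reader might infer that the planned final analysis will favour an arm with more deaths. The documents do not support that, because a death in a time-to-discharge analysis does not automatically receive the shortest time. This part of the reply stands. What remains is that the protocol still lists the durations, the SAP does not say that they are dropped, and its handling of death is open.

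A reader might also infer that the durations are to be fitted by a repeated-measures model with one value per patient. The protocol never assigns them to that model, and the SAP no longer uses it.

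A third tempting reading is that a patient who dies early gets the best possible score. For ICU days this is false, since a patient who never enters ICU scores 0. The supportable statement is that an early death scores shorter than a survivor who stays longer. The simulation covers hospital stay only.

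Finally, the consequences are limited. Death counts as non-response in the primary endpoint, scores 8 on the ordinal scale in Appendix B, and is reported as mortality through Day 60. Secondary endpoints are supportive and the SAP tests no formal hypothesis. All of this lowers the weight of the point. It does not make a length-of-stay result readable on its own when deaths differ between arms.

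**Conclusion.** The point holds in a limited form. The protocol durations lack a rule for death, and the rule that would apply to them as continuous endpoints leaves an early death with a short, favourable value. That conclusion rests on treating them as day counts, which is the natural reading but is not stated.

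The size is illustrative. The apparent advantage for the higher-mortality arm is 0.3 to 3.3 days in the fixed examples and 0.6 to 1.8 days in the simulated ones. Both size and direction depend on assumed mortality and on deaths occurring earlier than typical discharge. In the SAP the remaining gap is narrower: it does not say how deaths enter time to discharge, or what became of the two durations.

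**What to change.** In Protocol 3.2.2, replace the two durations with hospital-free days and ICU-free days from first dose through Day 28, with death by Day 28 scored 0. In 15.5, exempt them from the worst-observation rule. In 15.3, compare arms with a Hodges-Lehmann difference and confidence interval. List raw ICU and hospital days separately for survivors and for patients who die.

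In the SAP, either add these endpoints or state that they are dropped. For time to discharge, treat deaths as never discharged through the fixed horizon, or as a competing event.

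The cost is wording. The durations already come from the medical record, ICU status is recorded daily in hospital (Schedule of Events, footnote 13), and survival status is collected at Days 14, 28, 45 and 60. The small downside is that a free-days composite is less direct as a measure of resource use, which is why the raw days stay as a listing.
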